**Table JGDN.5.1. Censoring Rule of PFS Primary Analysis**

Situation	Event / Censor	Date of Event or Censor
Tumor progression or death	Event	Earliest date of PD or death
No tumor progression and no death	Censored	Date of last adequate radiological assessment or date of first study dose
unless		
No baseline radiological tumor assessment available	Censored	Date of first study dose
No adequate postbaseline radiological tumor assessment available and death reported after 2 scan intervals following first study dose	Censored	Date of first study dose
New anticancer treatment started and no tumor progression or death within 14 days	Censored	Date of adequate radiological assessment prior to (start of new therapy +14 days) or date of first study dose (whichever is later)
Tumor progression or death documented immediately after 2 or more consecutive missing scan intervals following last adequate radiological tumor assessment or first study dose (whichever is later)	Censored	Date of last adequate radiological assessment prior to the missing assessment or date of first study dose

Abbreviations: CR = complete response; PD = progressive disease; PFS = progression free survival; PR = partial response; SD = stable disease.

- a Symptomatic deteriorations (that is, symptomatic progressions, which are not radiologically confirmed) will not be considered as disease progressions.
- b Adequate radiological tumor assessment refers to an assessment with one of the following responses: CR, PR, SD, or PD.
- c The 2-scan interval is counted from the date of last adequate tumor assessment to the date of next 2 scheduled tumor assessments plus 14 days (adjusted by tumor assessment window).
- d Refer to flow chart in [Appendix 1](#) if a patient meets multiple censoring criteria.
- e If there are multiple dates associated with 1 assessment, the assessment date will be set to the first date when the overall response is PD and the last date otherwise.

**Overall survival (OS)** is defined as the time from the date of first study dose to death due to any cause. Patients will be censored at the date of last known alive.

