Vincristine: will be administered intravenously. Vincristine (patients \geq 10 kg: 1.5 mg/m², patients <10 kg: 0.05mg/kg. Dose is capped at 2 mg) is to be administered on Day 1 and Day 8 of each 21-day cycle.

Irinotecan: will be administered intravenously. Irinotecan (50 mg/m²) is to be administered on Days 1, 2, 3, 4, and 5 of each 21-day cycle.

Ifosfamide: will be administered intravenously. Ifosfamide (2.8 g/m²) is to be administered on Days 1, 2, 3, 4, and 5 of each 21-day cycle, for up to 6 cycles or a cumulative dose of 84 g/m².

Mesna: commercial formulations will be used and administered intravenously. Mesna should be administered at a minimum dose equal to 60% of the ifosfamide dose according to institutional guidelines.

Planned Duration of Treatment:

The planned duration of treatment is not fixed; patients will remain on study until they fulfill one of the criteria for study discontinuation.

Follow-up in post-treatment discontinuation: 30 days (\pm 7 days) for patients with disease progression. For patients who have discontinued study treatment due to toxicity or reasons other than progressive disease, follow-up will continue every 6 weeks (\pm 7 days) until progression.

Criteria for Evaluation:

Efficacy:

Radiographic assessments will be performed at baseline and then every 2 cycles (\pm 7 days) until radiographic documentation of progressive disease. Response Evaluation Criteria In Solid Tumors, Version 1.1 criteria should be used for all solid tumors with the exception of central nervous system tumors. Response Assessment in Neuro-Oncology Criteria or Macdonald Criteria should be used for central nervous system tumors.

Safety: The safety and tolerability of the study treatment is determined by reported adverse events (AEs), physical exam including vital signs, clinical laboratory tests, electrocardiograms, and results of echocardiogram / multigated acquisition scans. Adverse events will be coded using the Medical Dictionary for Regulatory Activities (MedDRA®) and graded using National Cancer Institute Common Terminology Criteria for Adverse Events (NCI-CTCAE) Version 4.0 and summarized by System Organ Class and preferred term.

Pharmacokinetic/Pharmacodynamic:

Blood samples will be collected at various time points for PK assessment for olaratumab levels and the levels of the combination chemotherapies. Blood samples will be collected at various time points for immunogenicity analysis.

Tailoring Genetics and Biomarkers:

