- The patient has radiographic progressive disease or significant symptomatic disease deterioration characterized as progression of disease, in the opinion of investigator, in the absence of radiographic evidence of progressive disease.
- The patient experiences unacceptable toxicity (for example, a persistent moderate toxicity that is intolerable to the patient).
- The patient is noncompliant with study procedures and/or treatment (Section 7.6).

The reason for and date of discontinuation will be collected for all patients. The date of discontinuation (for any of the above reasons) from study treatment is to be reported on the electronic case report form (eCRF). Patients who discontinue will have follow-up procedures performed as shown in the Study Schedule ([Attachment 1](#)).

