8.3. Efficacy Evaluations

A secondary objective of the study is to document any antitumor activity. Imaging studies and tumor assessments are to be obtained every 2 cycles (± 7 days), until documented progression for patients with complete response (CR), partial response (PR), or stable disease (SD).

For patients who have discontinued study treatment due to toxicity or reasons other than progressive disease, imaging studies and tumor assessments are to be obtained every 6 weeks (± 7 days) until progression. For these patients, details on subsequent anticancer treatment (start/stop dates and treatments administered) and first post-study treatment disease progression date should be recorded.

Each patient will be assessed by one or more of the following radiologic tests for tumor measurement:

- Computed tomography (CT) scan
- Magnetic resonance imaging (MRI)
- Chest x-ray

Each patient's full extent of disease will also be assessed with the following:

- Tumor measurement by RECIST v1.1 (Eisenhauer et al. 2009) should be used for all tumors with the exception of CNS tumors. RANO (Wen et al. 2010) or Macdonald (Macdonald et al. 1990) criteria should be used for CNS tumors.
- Evaluation of tumor markers, if indicated
- Evaluation of performance status (Lansky [Lansky et al. 1987] or Karnofsky [Karnofsky et al. 1948] scale)

To confirm objective responses, all lesions should be radiologically assessed, and the same radiologic method used for the initial response determination should be repeated at least 6 weeks (2 cycles) following the initial observation of an objective response, using the sample method that was used at baseline. If a patient is discontinued from the study, repeat radiology assessments may be omitted if clear clinical signs of progressive disease are present.

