Imaging Studies (CT/MRI)	X (if applicable)	X	For patients who have discontinued study treatment due to toxicity or reasons other than progressive disease, imaging studies and tumor assessments are to be obtained every 6 weeks (± 7 days) until progression or initiation of other anticancer therapy. RECIST v1.1 should be used for all tumors with the exception of CNS tumors; RANO or Macdonald criteria should be used for CNS tumors.
RECIST v1.1, RANO, or Macdonald Tumor Assessments	X (if applicable)	X	
Subsequent Anti-Cancer Treatments, and Associated Disease Progression Date		X	For all patients, details on subsequent anticancer treatment (start/stop dates and treatments administered) and first post-study treatment disease progression date should be recorded.
Other Assessments			
PK Sampling	X		See Attachment 4 for details.
Biomarker Sampling	X		

Abbreviations: AE = adverse event; CNS = central nervous system; CRF = case report form; CT = computed tomography; ECG = electrocardiogram; ECHO = echocardiogram; IRR = infusion-related reaction; MRI = magnetic resonance imaging; MUGA = multi-gated acquisition; PK = pharmacokinetics; RANO = Response Assessment in Neuro-Oncology; RECIST = Response Evaluation Criteria In Solid Tumors.

- a **Short-term follow-up** begins the day after the patient and the investigator agree that the patient will no longer continue study treatment and lasts approximately 30 days (± 7 days). The date of this agreement is to be reported on the CRF as the date of discontinuation from study treatment.
- b **Long-term follow-up** begins the day after short-term follow-up is completed. Patients that discontinue study treatment for reasons other than progression will be followed every 6 weeks (± 7 days) until progression.

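### Children stopped for symptomatic progression without a scan are censored rather than counted in PFS, which biases PFS upward; no sensitivity analysis shows by how much

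*SAP*

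**What the plan says.** Protocol 6.3.1 lists among the reasons to discontinue study drug "significant symptomatic disease deterioration characterized as progression of disease, in the opinion of investigator, in the absence of radiographic evidence of progressive disease".

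After discontinuation, Attachment 1 (Follow-up Assessments, note b) says "Patients that discontinue study treatment for reasons other than progression will be followed every 6 weeks", and Protocol 8.3 likewise limits off-treatment 6-weekly imaging to stops for toxicity or reasons other than progressive disease. For patients with progression the Synopsis gives "Follow-up in post-treatment discontinuation: 30 days" (± 7 days).

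The protocol is not consistent on whether a scan is expected after a symptomatic stop. The Synopsis asks for radiographic assessment "until radiographic documentation of progressive disease". Protocol 8.3 says that after discontinuation "repeat radiology assessments may be omitted if clear clinical signs of progressive disease are present", but that sentence closes the paragraph on confirming responses.

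SAP 5.3.2 defines PFS from first dose to radiologic progression or death from any cause. Note a to Table JGDN.5.1 adds: "Symptomatic deteriorations (that is, symptomatic progressions, which are not radiologically confirmed) will not be considered as disease progressions". A patient with neither event is censored at the last adequate radiological assessment, or at first dose if there is none. SAP 5.8 plans a Kaplan-Meier median with 90% CI by dose cohort and combination arm. The table is titled as the primary PFS analysis, but no other PFS analysis is named.

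**The concern.** The protocol treats symptomatic progression as progression when it decides who stops and who is followed. The SAP does not treat it as progression when it counts events. A child who falls between the two rules leaves the PFS risk set because the disease has worsened. Kaplan-Meier assumes that censored patients have the same outlook as those still at risk, and here they do not. The error has one direction: PFS looks longer.

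PFS is named in the secondary antitumor objective (Protocol 5.2.2) and will be reported in arms of about 20, where one or two misplaced patients show. The same unscanned children are kept as non-responders in the response-rate denominator (SAP 5.3.2), so the two efficacy summaries treat them differently.

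**Working it through.** The documents give no expected PFS, event count or symptomatic-progression rate for this trial, so there is no stated figure to reproduce.

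**Inputs from the documents.** Cycle of 21 days (Synopsis). Scan every 2 cycles (Protocol 8.3), so the first is due at 2 × 21 = 42 days, about Week 6. Follow-up of 30 ± 7 days after progression (Synopsis). About 20 evaluable patients per combination arm (Protocol 6.2).

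**Assumptions.** Exponential time to progression with median m = 6, 9, 12 or 18 weeks. A constant share s of progressions declared on symptoms and never scanned, 10% or 30%. A share d of those children whose death is captured within follow-up, 0 or 30%.

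**Step 1: where a child stopped on symptoms ends up.**
- A scan shows progression: event.
- No post-baseline scan, and a captured death within 2 scan intervals of first dose (2 × 42 + 14 = 98 days): event, unless the new-therapy rule applies.
- No captured death, at least one adequate post-baseline scan: censored at the last one.
- No captured death, no post-baseline scan: censored at first dose, adding nothing to the curve.

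**Step 2: expected number censored at Day 1.** With p = 1 − 2^(−6/m), the chance of progressing before Week 6, the number per 20 is 20 × s × (1 − d) × p. For m = 6, s = 30%, d = 0: 20 × 0.30 × 0.50 = 3.0. For m = 18, s = 10%, d = 0: 20 × 0.10 × 0.206 = 0.41.

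**Step 3: 12-week PFS with d = 0.** Of those progression-free at the start of a 6-week interval, a fraction p progress. The part s × p is censored back at the start of the interval and is no longer at risk at the next scan. The Kaplan-Meier factor per interval is (1 − p)/(1 − s·p), and 12-week PFS is its square. With symptomatic progression counted, 12-week PFS is (1 − p)². For m = 12, s = 30%: (0.7071/0.9121)² = 0.601, against 0.7071² = 0.500.

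| m (weeks) | p | Symptomatic PD counted | SAP rule, s = 10% | SAP rule, s = 30% | Day-1 censored per 20, s = 10% / 30% |
|---|---|---|---|---|---|
| 6 | 0.500 | 25.0% | 27.7% | 34.6% | 1.0 / 3.0 |
| 9 | 0.370 | 39.7% | 42.8% | 50.2% | 0.7 / 2.2 |
| 12 | 0.293 | 50.0% | 53.1% | 60.1% | 0.6 / 1.8 |
| 18 | 0.206 | 63.0% | 65.7% | 71.6% | 0.4 / 1.2 |

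The overstatement is 2.7 to 3.1 points at s = 10% and 8.6 to 10.5 points at s = 30%. Simulation gives the same values within sampling error.

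**Step 4: some of these children die in follow-up (d = 30%).** Simulated 12-week PFS at s = 30%, SAP rule against symptomatic progression counted: 32.4% vs 25.3% (m = 6), 47.8% vs 39.9% (m = 9), 58.1% vs 50.5% (m = 12), 70.0% vs 63.5% (m = 18). The gap is 6.5 to 7.9 points. At s = 10% it is 1.9 to 2.4 points for m = 9 to 18. Day-1 censoring falls by 30%.

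**Step 5: the planned summary, the median.** It moves largely in 6-week scan steps. In simulated trials of 20 with s = 30%, the SAP-rule median exceeded the alternative in 57% to 84% of trials across these values of m and d, and was never below it. Part of that gap arises because the alternative dates symptomatic events on the day they occur; the 12-week figures are free of this.

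**The case against.** Several points stand and limit the claim.

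- A reader might infer that the SAP counts only radiologic progression. It does not: death from any cause is an event, and an unscanned child whose death is captured within 98 days of first dose generally remains one. Capture is limited, though. Protocol 8.1.2.1 excludes progression-related deaths from SAE reporting unless possibly drug-related, and under 8.1.2.2.3 most patients leave the study after the 30-day visit.
- A reader might infer that the protocol freely lets sites skip the scan. The sentence on omission concerns repeat assessments, in a paragraph that opens "To confirm objective responses, all lesions should be radiologically assessed"; the Synopsis points the other way; and Attachment 1 lists imaging at the 30-day visit if applicable and asks for the first post-study progression date for all patients. The text supports ambiguity, not a general waiver. The mechanism needs only that no scan is clearly required.
- A reader might infer that many children are lost at Day 1, or that the bias is worst in the sickest arm. The documents give no rate for the first, and no between-arm test is planned that the second could distort. A constant share s does not test the second either.
- Efficacy is exploratory (SAP 5.3.2 and 5.8), radiologic PFS is an objective, prespecified definition, and sampling error is large: 8 of 20 has an exact 90% CI of 22% to 61%. A shift of 3 points is small beside that. It is still a bias, and it does not average out across arms.

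**Conclusion.** The mismatch between the protocol's stopping rule and the SAP's event definition is real, the resulting censoring is informative, and it raises PFS. That much follows from the text. The size rests on assumed inputs: about 2 to 3 points of 12-week PFS if 10% of progressions are symptomatic only; about 10 points if 30% are, or about 7 if 30% of those children die within follow-up. Some patients, roughly 0.4 to 3 of 20, would be censored at Day 1.

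The primary endpoint, DLT and PK exposure matching, is not touched. The documents do not support saying that radiologic PFS is the wrong definition, only that it should not stand alone here. The Appendix 1 flow chart for patients who meet several censoring rules was not available to check.

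**What to change.** Keep radiologic PFS as defined. In SAP 5.8 and Table JGDN.5.1 add a sensitivity Kaplan-Meier PFS in which investigator-declared symptomatic progression without radiologic progression is an event at the recorded discontinuation date. Report by arm the number stopped for symptomatic progression and the number censored at Day 1.

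The cost is one added analysis and two counts. Protocol 6.3.1 already has the reason and date of discontinuation collected, so no new data are needed. The downside is that symptomatic progression is a softer event, and the discontinuation date (the day patient and investigator agree to stop treatment, Attachment 1 note a) only approximates the progression date. Hence both results should be shown side by side.

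Separately, the Synopsis, Protocol 8.3 and Attachment 1 should be reconciled on whether imaging is expected after a symptomatic stop. No new imaging requirement is proposed.

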6.1.1. Inclusion Criteria

Patients may be included in the study if they meet all of the following criteria during screening prior to first dose of study drug.

- [1] The patient must have histological or cytological evidence of a diagnosis of solid tumor, excluding lymphomas and melanoma, but including central nervous system (CNS) tumors, that is relapsed or refractory, not be amenable to curative treatment, and for whom chemotherapy with doxorubicin, vincristine/irinotecan, or ifosfamide is deemed appropriate by the investigator. For patients with CNS tumors, neurologic deficits in patients with CNS tumors must have been stable for at least 7 days prior to study enrollment.
- [2] The patient has the presence of measurable and/or nonmeasurable but evaluable disease as defined by the Response Evaluation Criteria In Solid Tumors (RECIST Version 1.1) (Eisenhauer et al. 2009; refer to [Attachment 8](#)). Response Assessment in Neuro-Oncology (RANO) Criteria (Wen et al. 2010) or Macdonald Criteria (Macdonald et al. 1990) should be used for CNS tumors.
- [3] The patient is <18 years of age at the time of first dose of study drug.
- [4] The patient, or patient's parent/guardian, has given written informed consent and authorization for release of health information for research prior to any study-specific procedures being performed.
- [5] The patient has a Lansky (<16 years of age; Lansky et al. 1987) or Karnofsky (≥ 16 years of age; Karnofsky et al. 1948) performance score of at least 50.
- [6] The patient has adequate hematologic, organ, and coagulation function ≤ 2 weeks (14 days) prior to first dose of study drug:
 - Absolute neutrophil count (ANC) $\geq 750/\text{mm}^3$. Granulocyte colony-stimulating factor (G-CSF) cannot be administered ≤ 1 week (7 days) prior to first dose of study drug. Pegfilgrastim cannot be administered ≤ 2 weeks (14 days) prior to first dose of study drug.

- Platelets $\geq 75,000/\text{mm}^3$. Platelet transfusion to meet this enrollment criterion is not allowed within the preceding 5 days of first dose of study drug.
- Hemoglobin $\geq 8 \text{ g/dL}$. Transfusions with packed red blood cells is allowed.
- Total bilirubin (sum of conjugated + unconjugated) $\leq 1.5 \times$ upper limit of normal (ULN) for age.
- Alanine aminotransferase (ALT) and aspartate aminotransferase (AST) $\leq 3.0 \times$ ULN. If the liver has tumor involvement, AST and ALT equaling $\leq 5.0 \times$ ULN are acceptable.

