It is assumed that at each protocol-specified time point, a response assessment occurs. (When no imaging/measurement is done at all at a particular time point, the patient is not evaluable (NE) at that time point.) Table 1 provides a summary of the overall response status calculation at each time point for patients who have *measurable disease* at baseline.

Table 1. Time Point Response: Patients with Target (\pm Nontarget) Disease

Target Lesions	Non-Target Lesions	New Lesions	Overall Response
CR	CR	No	CR
CR	Non-CR/non-PD	No	PR
CR	Not evaluated	No	PR
PR	Non-PD or not all evaluated	No	PR
SD	Non-PD or not all evaluated	No	SD
Not all evaluated	Non-PD	No	NE
PD	Any	Yes or No	PD
Any	PD	Yes or No	PD
Any	Any	Yes	PD

Abbreviations: CR = complete response; PR = partial response; SD = stable disease.; PD = progressive disease; NE = inevaluable.

Table 2 is to be used when patients have *nonmeasurable* disease only.

Table 2. Time Point Response: Patients with Nontarget Disease Only

Nontarget Lesions	New Lesions	Overall Response
CR	No	CR
Non-CR/non-PD	No	Non-CR/non-PD ^a
Not all evaluated	No	NE
Unequivocal PD	Yes or No	PD
Any	Yes	PD

Abbreviations: CR = complete response; PD = progressive disease ; NE = inevaluable.

^a non-CR/non-PD is preferred over SD for nontarget disease.

Frequency of Tumor Re-Evaluation

A baseline tumor evaluation must be performed within 4 weeks before patient begins study treatment. Frequency of tumor re-evaluation while on and adapted to treatment should be protocol-specific and adapted to the type and schedule of treatment. In the context of Phase 2 studies where the beneficial effect therapy is not known, follow-up every 6-8 weeks is reasonable. Normally, all target and non-target sites are evaluated at each assessment using the same method. However, bone scans may need to be repeated only when CR is identified in target disease or when progression in bone is suspected.

Confirmatory Measurement/Duration of Response

Confirmation:

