The main goal of confirmation of objective response in clinical trials is to avoid overestimating the response rate observed. The confirmation of response is particularly important in *nonrandomized trials* where response (CR/PR) is the primary end point. In this setting, to be assigned a status of PR/CR, changes in tumor measurements must be confirmed by repeat assessments that should be performed no less than 4 weeks after the criteria for response are first met. To confirm a response of CR, a full assessment of all target and nontarget lesions that were present at baseline must occur, including those measured by bone scan. To confirm a PR or SD, a full assessment of target lesions that were present at baseline must occur; assessment of nontargets is not required.

However, in *randomized trial* (Phase 2 or 3) or studies where SD or progression is the primary endpoints, confirmation of response is not required. But, elimination of the requirement may increase the importance of central review to protect against bias, in particular of studies which are not blinded.

In the case of SD, follow-up measurements must have met the SD criteria at least once after start of treatment at a minimum interval not less than 6 weeks measured from first dose.

Duration of Overall Response

The duration of overall response is measured from the time measurement criteria are first met for CR or PR (whichever is first recorded) until the first date that disease is recurrent or objective progression is observed (taking as reference for PD the smallest measurements recorded on study).

The duration of overall CR is measured from the time measurement criteria are first met for CR until the first date that recurrent disease is objectively documented.

Duration of Stable Disease

Stable disease is measured from the start of the treatment (in randomized trials, from date of randomization) until the criteria for objective progression are met, taking as reference the smallest sum on study (if the baseline sum is the smallest, that is the reference for calculation of PD).

Independent Review of Response and Progression

When objective response (CR + PR) is the primary end point, and when key drug development decisions are based on the observation of a minimum number of responders, it is recommended that all claimed responses be reviewed by an expert(s) independent of the study. If the study is a randomized trial, ideally reviewers should be blinded to treatment assignment.

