### **5.3.2. Efficacy Variables**

The study was not designed to make an efficacy assessment. However, any tumor response data will be tabulated according to study part and patient cohort.

Exploratory efficacy analysis will be performed to investigate antitumor activity within each combination arm. Response and disease progression will be evaluated using Response Evaluation Criteria in Solid Tumors (RECIST) version 1.1 (Eisenhauer et al. 2009) for all tumors with the exception of CNS tumors. RANO (Wen et al. 2010) or Macdonald (Macdonald et al. 1990) criteria should be used for CNS tumors.

**Overall Response Rate (ORR)** is defined as the percentage of patients achieving a best overall response of either Complete Response (CR) or Partial Response (PR), as determined by RECIST 1.1/RANO/Macdonald criteria. The best overall response is the best response from the start of the treatment until PD/recurrence.

**Disease control rate (DCR)** is defined as the percentage of patients achieving a best overall response of CR, PR, or SD. Patients who do not have any postbaseline tumor response assessments for any reason are considered non-responders and are included in the denominator when calculating the response rate.

**Duration of Overall Response** is measured from the time measurement criteria are first met for CR or PR (whichever is first recorded) until the first date the criteria is met for PD is objectively documented, or initiation of other/additional antitumor therapy is first reported, or death. Patients who do not relapse are censored at the day of their last tumor assessment.

**Progression-free survival (PFS)** is defined as the time from the date of first study dose to the first date of radiologic disease progression or death due to any cause. [Table JGDN.5.1](#) defines the rules of censoring to be applied to PFS.

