## 5.8. Efficacy Analyses

The study was not designed to make an efficacy assessment. Exploratory efficacy analysis will be performed to investigate antitumor activity within each combination arm. The efficacy analysis will include all treated patients (ie. Safety Population). Tumor response data will be tabulated according to dose cohort and combination arm. A listing of best overall response will be provided by cohort. Best overall response will be summarized by dose cohort and combination arm. The objective response rate (ORR=CR+PR) and disease control rate (DCR=CR+PR+SD) along with the 90% exact confidence interval (CI) will be tabulated for each cohort and combination arm. For patients having CR/PR, the median duration of response,

together with a 90% CI will be estimated using Kaplan-Meier method. The median PFS will be estimated along with 90% CI by dose cohort and combination arm, using Kaplan-Meier method.

Any deaths observed during the study will be summarized descriptively and possibly interpreted in the context of study drug dose for each patient observed to have died. Dependent on the maturity of the data, overall survival may be analyzed using time-to-event methods, such as Kaplan-Meier.

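### SAP Table JGDN.5.1 note b and the DCR definition omit Non-CR/non-PD, so read literally a progression-free patient rated that way throughout is censored for PFS at first dose and counted as a DCR failure

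*SAP*

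**What the plan says.** **Who can enter.** Protocol 6.1.1, criterion [2]: "The patient has the presence of measurable and/or nonmeasurable but evaluable disease". A patient with no measurable lesion is therefore eligible.

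**How their scans are rated.** Protocol Attachment 8, Table 2, covers patients with non-target disease only. Its possible overall responses are CR, Non-CR/non-PD, NE and PD. It has no SD row, and the footnote says "non-CR/non-PD is preferred over SD for nontarget disease".

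**PFS.** SAP Table JGDN.5.1, note b: "Adequate radiological tumor assessment refers to an assessment with one of the following responses: CR, PR, SD, or PD". For a patient with neither progression nor death, the censoring date is "Date of last adequate radiological assessment or date of first study dose". A separate row censors at first dose when there is no adequate post-baseline scan and death is reported after two scan intervals. Note c adds: "The 2-scan interval is counted from the date of last adequate tumor assessment".

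**DCR.** SAP 5.3.2 says it "is defined as the percentage of patients achieving a best overall response of CR, PR, or SD". SAP 5.8 repeats CR+PR+SD, uses all treated patients as the denominator, and asks for a 90% exact confidence interval by cohort and combination arm. Protocol 10.7 defines DCR the same way.

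No legible text in the SAP says that Non-CR/non-PD is to be treated as SD.

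**The concern.** The protocol admits a group of patients and gives them their own label for a non-progressing scan, and the SAP's two lists of acceptable responses then leave that label out. Such a scan is neither adequate for PFS nor a success for DCR.

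The group is plausible in this trial. Attachment 8 classes blastic bone lesions, effusions, lesions below 10 mm and irradiated lesions without later progression as non-measurable, and Protocol 6.2 aims for at least 10 osteosarcoma patients.

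The PFS error is not random. The follow-up removed belongs to the members of this group who stay progression-free longest, so the Kaplan-Meier curve is pulled down. DCR is pulled down because patients with disease control stay in the denominator and leave the numerator. Two programmers following the same SAP could also report different results, since Attachment 8 has best overall response computed by an algorithm from the investigators' time-point ratings.

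**Working it through.** The documents contain no figure that depends on this point, so there is nothing to reproduce. The check applies the rules in order and then sizes the effect.

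**1. Apply the rules to a non-CNS patient with only non-measurable disease and every scan rated Non-CR/non-PD.**

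- Alive without progression: no post-baseline scan is adequate, so PFS is censored at first dose. By the SAP duration formula (end - start + 1) that is 1 day.
- Death after two scan intervals: also censored at first dose. Scans are every 2 cycles (42 days) and note c adds 14 days, so the window is 2 x 42 + 14 = 98 days.
- DCR: in the denominator, not in the numerator.
- Depends on interpretation: if a non-adequate scan counts as a missing interval, as note c suggests by counting from the last adequate assessment, then PD first seen at scan 3 (3 x 42 = day 126) or later is also censored at first dose.

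Not affected: PD at scan 1 or 2, death by day 98, CR in non-target disease, CNS tumors rated by RANO or Macdonald, and ORR.

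**2. Assumptions for size.** The share with only non-measurable disease is taken as 10%, 20% or 30%. True median PFS m is 12, 18 or 28.6 weeks; 18.0 and 28.6 are the adult-study medians in Protocol 5.3, and 12 is an assumption. PFS is exponential.

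**3. DCR.** The fraction of the group without PD at the week-6 scan is 2^(-6/m). The largest possible loss is share x 2^(-6/m), less any CRs.

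| m (weeks) | 2^(-6/m) | Loss at 10% | Loss at 30% |
|---|---|---|---|
| 12 | 0.707 | 7.1 points | 21.2 points |
| 18 | 0.794 | 7.9 points | 23.8 points |
| 28.6 | 0.865 | 8.7 points | 26.0 points |

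For one arm of 20 (the target in Protocol 6.2), each such patient moves DCR by 1/20 = 5 points. If 12 are truly controlled and 3 of them are rated Non-CR/non-PD, the Clopper-Pearson 90% intervals are:

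- all counted: 12/20 = 60% (39.4% to 78.3%)
- literal rule: 9/20 = 45% (25.9% to 65.3%)

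**4. PFS.** Simulation with 400,000 patients per case, scans every 6 weeks, PD dated at the scan, and follow-up uniform from 12 to 78 weeks (an assumption). Entries are Kaplan-Meier PFS at 24 weeks for shares of 10/20/30%.

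| m (weeks) | Correct | Only patients without PD moved to first dose | PD at scan 3 or later also moved |
|---|---|---|---|
| 12 | 0.249 | 0.240 / 0.231 / 0.221 | 0.236 / 0.222 / 0.204 |
| 18 | 0.397 | 0.383 / 0.369 / 0.355 | 0.381 / 0.363 / 0.343 |
| 28.6 | 0.559 | 0.543 / 0.524 / 0.503 | 0.545 / 0.526 / 0.504 |

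The fall at a 10% to 30% share is 0.009 to 0.028, 0.014 to 0.042 and 0.016 to 0.056 for the three medians under the first reading. Under the second it is 0.013 to 0.045, 0.016 to 0.054 and 0.014 to 0.055, and 4.1-12.3%, 5.0-15.0% and 5.8-17.3% of the arm's events are lost.

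A separate simulation with other assumptions (medians of 60 to 200 days, follow-up of 60 to 500 days) gave a fall in 6-month PFS of about 0.6 to 6 points under the first reading, for example 37.8% to 34.8% at a median of 120 days and a 20% share.

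**The case against.** The sponsor may mean SD to cover every non-progressing scan. Protocol 8.3 speaks of imaging patients in CR, PR or SD with no separate group for non-measurable disease. The Attachment 8 footnote states a preference, so a site or the response algorithm could record SD. This is a fair account of possible intent, but the footnote separates the two labels and the SAP never joins them. It limits certainty about what will be programmed and leaves the written rule as it is.

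A scan that was done and rated is not obviously missing, so the effect on PD at scan 3 or later is doubtful. That stands: the event-loss figures apply only under that reading. The Appendix 1 flow chart could not be read in the text available, and its absence is no fault of the plan. Note d sends the reader there only when several censoring criteria apply, so it does not govern the simple case of no progression and no death, nor DCR.

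The endpoints are minor. The SAP says the study was not built to assess efficacy, no dose decision uses PFS or DCR, and DCR is named in no objective. The listing of best overall response in SAP 5.8 would let a reader recompute DCR. The PFS shift, at most about 0.056, is small beside a simple binomial 90% half-width of 0.16 to 0.18 for 20 patients. All of this stands and limits the importance. It does not justify a rule that gives the wrong answer for eligible patients, and PFS is named in a secondary objective (Protocol 5.2.2).

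**Conclusion.** The concern holds. As written, note b and the DCR definition misclassify progression-free non-CNS patients whose scans are rated Non-CR/non-PD, and both errors lower the estimate. DCR takes the larger effect: 5 points per such patient in an arm of 20, and at most 7 to 26 points over the assumed range. The fall in 24-week PFS is about 0.01 to 0.06. These sizes rest on an assumed 10-30% share, exponential PFS, assumed follow-up, and medians partly borrowed from adults with soft tissue sarcoma, so they are illustrations. The finding about the rule rests on the text alone. The point should be corrected, but it does not touch the primary DLT and PK endpoint.

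**What to change.** In SAP Table JGDN.5.1 note b, list the adequate responses as CR, PR, SD, Non-CR/non-PD or PD, and check that the Appendix 1 flow chart agrees.

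In SAP 5.3.2 and 5.8, count a best overall response of Non-CR/non-PD as disease control. Apply the condition that Attachment 8 sets for SD: the criteria must have been met "at a minimum interval not less than 6 weeks measured from first dose". If the sponsor prefers another treatment of these patients, such as DCR in measurable disease only, the SAP should say so.

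The cost is one category in each of two definitions, one check of the flow chart and one programming condition. No new data are needed, and Protocol 10.7 already leaves such detail to the SAP.
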